6.3. Missing Data

No imputation will be carried out for missing data or subjects who withdraw early. Data from children withdrawn because of failure to respond to the usual management of SAM, or voluntary dropouts will be included in the analysis up to the time of withdrawal. A supplementary analysis excluding the children withdrawn may be performed.

An exception to this is the Mean Breast Feeding Frequency variable for the Weight Gain analysis. In cases where there were missing values for all ten days, the mean value was imputed to be 0 rather than missing for modelling purposes.

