9.2. Time (days) to discharge from acute phase

Derivations

Discharge from the acute phase is based on improvement in mental state, normalisation of vital signs, re-establishment of oral feeding and resolution of all acute illnesses.

The CRF collects information on whether a patient is ready for discharge from the acute phase (Y/N) daily. Time (days) will be derived as the number of days between baseline and the first occurrence where 'Ready for discharge from acute phase' was recorded as Yes. Baseline will be taken as the earliest measurement recorded in the daily monitoring chart. Day will be derived relative to the baseline.

If a subject withdrew or died before being ready for discharge from the acute phase then they will be censored at the time they left the study. Patients who completed Day 10 before being ready for discharge will be followed up by the site until they withdraw or are ready for discharge.

Kaplan Meier

A Kaplan-Meier plot including 95% CIs and the number of subjects at risk at each day will be presented.

Cox Proportional Hazards

The time to discharge from acute phase will be compared between treatment groups using a Cox's Proportional Hazards model adjusting for the covariates specified in Section 7.1.

The time to discharge from acute phase will be presented in quartiles for each group. The hazard ratio, 95% CI and associated p-value will also be presented.

Residual plots from the Cox proportional hazard model and the Kaplan-Meier plot will be used to visually check the assumption of proportional hazards is fair. If the proportional hazard assumption is invalid, then other methods of analysis may be considered which do not make this assumption, for example a Weibull model may be fitted to the data.

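### Time to discharge censors children who die, so the Kaplan-Meier curve overstates the proportion discharged and the upper quartile can be too early

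*SAP*

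**What the plan says.** SAP Section 9.2 defines the event as "the first occurrence where 'Ready for discharge from acute phase' was recorded as Yes", with time counted in days from baseline. Children who "withdrew or died before being ready for discharge from the acute phase then they will be censored at the time they left the study". Follow-up has no fixed end: "Patients who completed Day 10 before being ready for discharge will be followed up by the site until they withdraw or are ready for discharge".

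Three outputs follow:

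- a curve: "A Kaplan-Meier plot including 95% CIs and the number of subjects at risk at each day will be presented";
- a descriptive summary: "The time to discharge from acute phase will be presented in quartiles for each group";
- a comparison: "The time to discharge from acute phase will be compared between treatment groups using a Cox's Proportional Hazards model", with hazard ratio, 95% CI and p-value.

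Section 6.3 shows that withdrawals are of two kinds: "Data from children withdrawn because of failure to respond to the usual management of SAM, or voluntary dropouts will be included in the analysis". Such children contribute only until they leave. The only fallback there is optional: "A supplementary analysis excluding the children withdrawn may be performed".

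Section 8.1 tabulates completion and reasons for premature withdrawal by treatment group in the Safety population. It does not name death as a category. The SAP has no cumulative incidence or competing-risk analysis, and names no mortality endpoint or mortality table.

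**The concern.** Kaplan-Meier censoring assumes that a child who leaves the risk set would later have been discharged at the same pace as those who remain. That is impossible after death. The estimator hands the dead child's share to the survivors, and the curve climbs towards 100% however many children died.

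At stake is what a reader takes from the curve and quartiles: what share of admitted children became ready for discharge, and by when. If one arm had more deaths but the same discharge rate among children still in the acute phase, the two curves and the hazard ratio would look alike although fewer children in that arm were discharged. The optional analysis in Section 6.3 does not help, because it removes withdrawn children instead of counting them as not discharged.

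**Working it through.** **Is there a figure to reproduce?** No. The SAP gives no discharge rate, death rate, non-response rate or event count for this endpoint. All rates below are assumptions.

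**Direction, without assumptions.** Let dN/Y be the discharges divided by the children at risk at each event time.

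- One minus Kaplan-Meier = sum of KM(t−) × dN/Y, where KM ignores deaths.
- Cumulative incidence (Aalen-Johansen) = sum of S(t−) × dN/Y, where S is the probability of being neither discharged nor dead.

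S is never above KM, so one minus Kaplan-Meier is never below the cumulative incidence, and it exceeds it once a discharge follows a death. Quartiles read from the Kaplan-Meier curve can therefore only be too early or unchanged.

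**Size, under constant hazards.** Inputs (assumed): discharge hazard 0.2 per day; share s dying before discharge 2%, 5% or 10%, which gives a death hazard of 0.2 × s/(1 − s).

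- One minus Kaplan-Meier: 1 − exp(−0.2t). This is 1 − exp(−2) = 86.5% at Day 10 and 1 − exp(−6) = 99.8% at Day 30, whatever s is.
- Cumulative incidence: (1 − s) × [1 − exp(−0.2t/(1 − s))]. For s = 10% at Day 10: 0.9 × [1 − exp(−2.222)] = 80.2%.
- Time at which a proportion p is discharged: −ln[1 − p/(1 − s)] × (1 − s)/0.2. For s = 10% and p = 0.75: −ln(0.1667) × 4.5 = 8.06 days.

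| | SAP method | s = 2% | s = 5% | s = 10% |
|---|---|---|---|---|
| Discharged by Day 10 | 86.5% | 85.3% | 83.4% | 80.2% |
| Discharged by Day 30 | 99.8% | 97.8% | 94.8% | 89.9% |
| Lower quartile (days) | 1.44 | 1.44 | 1.45 | 1.46 |
| Median (days) | 3.47 | 3.50 | 3.55 | 3.65 |
| Upper quartile (days) | 6.93 | 7.10 | 7.40 | 8.06 |

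The overstatement is 1.2, 3.1 and 6.3 points at Day 10, and 2.0, 5.0 and 9.9 points at Day 30 (differences of the rounded entries).

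**Two arms.** Suppose the arms share the discharge hazard of 0.2 per day, and 5% die in one and 10% in the other. The expected Kaplan-Meier curves and quartiles are the same and the cause-specific hazard ratio is 1. The proportions discharged are 83.4% against 80.2% at Day 10, and 94.8% against 89.9% at Day 30.

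**Other rates.** A whole-day version uses a daily discharge probability a, with one minus Kaplan-Meier = 1 − (1 − a)^10 at Day 10:

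| a | SAP method, Day 10 | Cumulative incidence at Day 10 for s = 2%, 5%, 10% | Upper quartile, SAP method | Upper quartile from cumulative incidence for s = 2%, 5%, 10% |
|---|---|---|---|---|
| 0.10 | 65.1% | 64.6%, 63.8%, 62.3% | Day 14 | Day 14, 15, 16 |
| 0.15 | 80.3% | 79.4%, 78.0%, 75.5% | Day 9 | Day 9, 10, 10 |
| 0.20 | 89.3% | 88.0%, 86.1%, 82.7% | Day 7 | Day 7, 7, 8 |

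The lower quartile and median do not move in any of these nine cases. As an extreme, at a = 0.15 with 30% never discharged, the true upper quartile is not reached, while the SAP method still reports Day 9.

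**The case against.** Four points can fairly be made for the plan.

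- **Deaths may be visible elsewhere.** A reader might infer that the plan hides a mortality difference. The documents do not support that. No death rate is given, so no difference is known to exist, and the disposition table in Section 8.1 may show deaths by arm as a withdrawal reason. What stands is narrower: the discharge outputs alone would not show such a difference.
- **The hazard ratio is sound.** With deaths censored, Cox estimates a cause-specific hazard ratio for discharge, which is a legitimate quantity. Section 9.2 never reads it as an effect on the proportion discharged. What stands is a matter of labelling.
- **Withdrawal for failure to respond is not death.** It is tempting to treat both as competing events. Such a child could still recover after leaving, so this is possibly informative censoring, and coding the child as never discharged is itself an assumption. It belongs in a sensitivity analysis. Censoring voluntary dropouts is standard.
- **The stakes are modest.** This is one of several secondary endpoints, and Section 6 deems all analyses exploratory. At 2% mortality the error at Day 10 is about one point, and times are recorded in whole days.

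These points limit the finding but do not remove it: no other section corrects the curve or the upper quartile.

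**Conclusion.** The point holds for death, for the Kaplan-Meier curve and for the upper quartile. The direction follows from the estimator and needs no assumption. The size does: with a constant discharge hazard of 0.2 per day and 2% to 10% dying first, the overstatement is about 1 to 6 points at Day 10 and 2 to 10 points at Day 30, and the upper quartile should read 7.1 to 8.1 days instead of 6.9. The lower quartile and median are essentially unaffected, so it would be wrong to conclude that all the quartiles are materially biased. If deaths are very few, the practical effect is small. The change is still worth making because it is cheap and the curve would then show what it appears to show.

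**What to change.** In Section 9.2:

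1. Treat death before readiness for discharge as a competing event, not as censoring.
2. Replace the Kaplan-Meier plot and quartiles with the Aalen-Johansen cumulative incidence of discharge by arm, with 95% CIs. Read the quartiles from it and report not reached where that applies.
3. Keep the Cox model with its covariates, labelled as a cause-specific hazard ratio for discharge.
4. Report the number of deaths by arm beside these outputs. Use the Safety population, because the ITT definition in Section 4 requires a post-baseline measure and would omit a child who died before one.
5. Add a sensitivity analysis that also counts withdrawal for failure to respond as not discharged. Continue to censor voluntary dropouts.

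A Fine-Gray model is optional. It is a choice of estimand, since its ratio mixes effects on discharge and on death.

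The cost is SAP wording and standard code. Reasons for withdrawal are already to be summarised under Section 8.1, so no new data collection appears necessary. The downside is one more estimate to explain for an exploratory secondary endpoint.

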2. STUDY DESIGN

Please refer to the protocol for details on the study design and sample size.

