6. GENERAL CONSIDERATIONS FOR DATA ANALYSES

All programming will be performed using - SAS (version 9.4 or later), SPSS or STATA. The analysis will be carried out in collaboration with icddr,b, and Stanford University. Further analysis of the SCORDoK score may be carried out by the Denmark SCORDoK team. The metabolomic data will be analyzed by the CRO assaying the samples (Metabolon) with input from representatives from the R&D Platform Technology & Science group within the GSK subsidiary company Cellzome All analyses will be deemed exploratory.

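### The only fallback named for non-proportional hazards in time to discharge, a Weibull model, is itself a proportional hazards model unless its shape parameter differs by arm

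*SAP*

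**What the plan says.** Time to discharge from the acute phase is the first secondary endpoint listed in SAP Section 1.2. Section 9.2 sets out its analysis in four steps.

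- Main model: "The time to discharge from acute phase will be compared between treatment groups using a Cox's Proportional Hazards model adjusting for the covariates specified in" a cross-referenced section. The covariates are in Table 1 under Section 6.1: baseline weight-for-length Z score, age and sex, alongside treatment.
- Reported effect: "The hazard ratio, 95% CI and associated p-value will also be presented". Quartiles of time to discharge are given for each group, and a Kaplan-Meier plot with 95% CIs and daily numbers at risk is also planned.
- Check: "Residual plots from the Cox proportional hazard model and the Kaplan-Meier plot will be used to visually check the assumption of proportional hazards is fair".
- Contingency if the check fails: "other methods of analysis may be considered which do not make this assumption, for example a Weibull model may be fitted to the data".

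Nothing else in the SAP describes the Weibull model. Table 1 lists only Cox for this endpoint. The SAP does not mention an arm-specific shape, a time-varying treatment effect, a log-normal or log-logistic model, or restricted mean time.

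**The concern.** The sentence states a sound rule, which is to use a method free of the failed assumption, and then gives an example that breaks it. An analyst who has just judged proportional hazards untenable, and who takes the one model named, would fit something that imposes the same constant ratio. It would also replace Cox's free baseline hazard with a parametric one.

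At stake is the reading of the discharge result in the one situation the sentence was written for. A Weibull hazard ratio reported as the remedy would look like a correction while carrying the same restriction. An early benefit followed by a late reversal, or the opposite, would again be averaged into one number.

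**Working it through.** The SAP gives no figure to reproduce here. The point is a property of the model and does not depend on sample size, for which Section 2 defers to the protocol ("Please refer to the protocol for details on the study design and sample size").

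**1. The Weibull hazard ratio.** Let treatment x (0 or 1) act on the scale, with one shape k:

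h(t|x) = (k/λₓ)(t/λₓ)^(k−1), with λₓ = exp(a + bx).

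Dividing the arms, the factor t^(k−1) cancels:

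h(t|1)/h(t|0) = (λ₀/λ₁)^k = exp(−bk).

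No t remains, so this is proportional hazards. With illustrative values b = −0.2 and baseline scale 6 days, the ratio evaluated at days 1, 2, 4, 6, 8 and 10 is the same on every day:

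| Shape k | Ratio on every day | exp(−bk) |
|---|---|---|
| 0.7 | 1.1503 | 1.1503 |
| 1.0 | 1.2214 | 1.2214 |
| 1.5 | 1.3499 | 1.3499 |
| 2.5 | 1.6487 | 1.6487 |

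**2. Models that do relax it.** Under illustrative parameters, the hazard ratio at day 1 and day 10 is:

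| Model | Day 1 | Day 10 |
|---|---|---|
| Log-logistic, shape 2, scale 5 v 6 days | 1.42 | 1.09 |
| Log-normal, SD 0.6 on the log scale, median 5 v 6 days | 2.37 | 1.17 |
| Weibull, shape 1.8 (scale 5) v 1.0 (scale 6) | 0.60 | 3.76 |

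The last row shows that a Weibull model with arm-specific shapes is not proportional hazards.

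**3. Illustration of the consequence.** All inputs are assumptions, since the SAP has none: control hazard 0.15 per day; true ratio 2.0 up to day 4 and 0.5 afterwards; no other censoring before the cut-off.

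- Cox and common-shape Weibull, fitted to simulated data with 400,000 per arm and censored at day 20: 1.21 and 1.19.
- The same, censored at day 10: 1.40 and 1.39.
- A variant with control hazard 0.20, 20,000 per arm, censored at day 10: Weibull shape 0.88 and a single ratio of 1.48.

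I checked the first two by numerical integration. The Cox limit solves the expected partial-likelihood score equation, and the Weibull limit maximises the expected log-likelihood. This gave 1.20 and 1.18 at day 20, and 1.40 and 1.39 at day 10. In each case neither model shows that the ratio moved from 2.0 to 0.5.

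**4. Restricted mean time to day 20, exact, same inputs.**

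- Control: (1 − e^(−0.15×20))/0.15 = (1 − 0.0498)/0.15 = 6.335 days.
- Emollient, days 0 to 4 (hazard 0.30): (1 − e^(−1.2))/0.30 = 0.6988/0.30 = 2.329 days.
- Emollient, days 4 to 20 (hazard 0.075): e^(−1.2) × (1 − e^(−0.075×16))/0.075 = 0.3012 × 0.6988/0.075 = 2.806 days.
- Difference: 2.329 + 2.806 − 6.335 = −1.20 days.

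This summary remains well defined whether or not the hazards are proportional.

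**The case against.** The strongest reply is that the SAP does not commit to a Weibull model. The governing instruction is to use a method without the assumption. Weibull is an example, and both verbs in the sentence are permissive. An analyst could follow the rule with any suitable method and not depart from the plan. This stands, and it makes the fault a wrong example inside a correct rule. It does not clear the text, because Weibull is the only method named.

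Secondly, the model is not specified further, and a version with the shape varying by arm would not be proportional hazards. This is true as mathematics and limits the claim. The natural reading is still the common-shape model, since Section 6 names only general packages ("All programming will be performed using - SAS (version 9.4 or later), SPSS or STATA") and a plain Weibull regression in them has one shape by default. Reporting a time ratio would not help: with a common shape it re-expresses the same constant hazard ratio.

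Thirdly, the Kaplan-Meier plot and the quartiles are presented in any case, and the fallback is reached only after plots have shown a problem. A reader might infer that the fallback would conceal a reversal altogether or leave the discharge result invalid. The SAP does not support that: these outputs would let a reader see changing separation between the arms. What would mislead is the single ratio offered as the remedy.

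Finally, the stakes are low. Section 6 states that "All analyses will be deemed exploratory", the endpoint is secondary, and the weight-gain analysis is untouched. This stands and sets the severity.

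**Conclusion.** The example in Section 9.2 is wrong as written. A common-shape Weibull regression assumes proportional hazards and adds a parametric baseline, so the only named fallback would not relax the failed assumption unless its shape varies by arm. This follows from the algebra and rests on no trial data.

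The size is minor to moderate. The error takes effect only if the visual check fails and the analyst then picks the named example. A reader might infer that the plan fixes an invalid analysis in advance; it does not, because the choice is left open and the stated criterion is right. The ratios of about 1.2 and 1.4 and the −1.20 days come from one chosen crossing-hazards case. They show the mechanism and do not estimate the effect in this trial. They also move with the cut-off, which the SAP does not supply, since Section 9.2 follows children not ready by Day 10 until they are ready or withdraw.

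**What to change.** Replace the Weibull example with a method that does not assume proportional hazards, and keep the Table 1 covariates. For instance: if proportional hazards is not supported, report the difference between arms in restricted mean time to discharge up to a day fixed before the analysis, adjusted for baseline weight-for-length Z score, age and sex, with 95% CI. A Cox model with those covariates and a treatment-by-time term is an alternative; the form of the time term should then be stated. Log-normal or log-logistic models also drop proportional hazards, but each assumes a constant time ratio, so they may fit crossing hazards poorly. If Weibull is retained, say that its shape parameter differs by treatment arm.

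The horizon has to be written in as a number, because follow-up for this endpoint can run past Day 10.

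The cost is one sentence in Section 9.2. It needs no new data and no change to the design or to the main Cox analysis.

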9.3. Rate of suspected nosocomial infections

Derivations

Any new sign of infection during hospital stay that was not present at admission or not present for last 48 hours of hospital stay will be considered as nosocomial infection. Occurrence of the following four suspected nosocomial infections, pneumonia, fever, UTI and sepsis, is collected on the CRF. Subjects will be considered as having had a suspected nosocomial infection if they have at least one of these four infections where symptoms started during the 10-day treatment period. Pneumonia, fever, UTI and sepsis were identified during the interim results meeting as the key nosocomial infections of interest.

Summary Statistics

The number and percentage of subjects who have at least one suspected nosocomial infection during the 10 day treatment period will be summarised by treatment group. In addition the total number of infections (1, 2, 3, >3) and the type of infection will be summarised as frequency counts and percentages.

Following the interim analysis, nosocomial infections will also be summarised by age category.

Logistic Regression

The proportion of subjects who have at least one suspected nosocomial infection in each treatment group will be compared using a logistic regression. Covariates/ factors will be included in the model as described in Section 7.1Error! Reference source not found.. The odds ratio with associated 95% CI will be presented.

This analysis may not be performed if there are a low number of suspected nosocomial infections.

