1.2. Endpoint(s)

This is an exploratory open-label study to evaluate potential benefits of topical application of (SSO in SAM. There is little or no historical data available on efficacy endpoints, therefore an interim analysis was planned when 100 evaluable subjects have completed the study. The results from the interim analysis will help identify key/primary efficacy endpoints. Therefore, the list of endpoints and analysis plan may be updated after the interim analysis.

The endpoints which will be investigated in the analysis are:

Primary Endpoints

• Weight gain (g/kg/day)

Secondary Endpoints

- Time (days) to discharge from acute phase
- Rate of suspected nosocomial infections (nosocomial infection will be diagnosed clinically as per hospital's management guidelines where it has been mentioned that any new sign of infection during hospital stay that was not present at admission will be considered as nosocomial infection. Following the interim analysis, the list of nosocomial infections was restricted to pneumonia, fever, UTI and sepsis.)
- Change from baseline in transepidermal water loss (TEWL) at Day 10
- Change from baseline in plasma fatty acid levels at Day 10*
- Change from baseline in c-reactive protein (CRP) at Day 10
- Change from baseline in pro-inflammatory cytokine parameters at Day 10

- Clinical improvement of visual skin condition:
 - Change from baseline in skin redness at Day 10
 - \circ Change from baseline in skin condition score at Day 10
- Change from baseline in the skin and gut microbiome data at Day 10*
- * Change from baseline in plasma fatty acid levels at day 10 will not be included in the interim analysis as the results will not be available until the end of the study. The analysis of plasma fatty acid levels will be included in the final study report. However, this analysis is outside the scope of this RAP.
- * Change in the skin and gut microbiome data will be collected for a sub-sample of subjects in the study as described in the protocol amendment. This analysis will be performed at the end of the study by an external expert at Stanford University. The metabolomic data will be analysed by the CRO (Metabolon) and additional support will be provided by the GSK subsidiary company Cellzome. As previously indicated, the analysis of skin and gut microbiome data is outside the scope of this RAP.

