8.3. Baseline Characteristics

Summary statistics for the weight-for-length Z (WLZ) score, length-for-age Z (LAZ) score, weight-for-age Z (WAZ) score, mid upper arm circumference, mother's / caregiver's formal years of education, father's formal years of education and duration of exclusive breast feeding at Day 0 will be summarised by treatment group for the Safety population. The number and percentage of subjects will also be presented for, presence of oedema, breast feeding history (no breast feeding since birth, partial breast feeding or exclusive breast feeding), breast feeding status (still breast feeding, not still breast feeding), type of diarrhoea and presence of pneumonia, sepsis/septicaemia, meningitis/encephalitis, vitamin A deficiency, skin infection, ileus, ASOM/CSOM, enteric fever and other clinical diagnosis and visible wasting at Day 0.

For the interim analysis only, differences between the two treatment groups (emollient therapy versus no emollient) for each baseline characteristic will be examined. For continuous data a two sample t-test will be carried out to compare the two treatment groups. If the data is not normally distributed then a non-parametric Wilcoxon rank sum test may be used instead. For categorical data a chi-squared test will be used.

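### Section 9.3 scores suspected nosocomial infection as ever/never over 10 days with no allowance for time observed, so event-free early leavers count as uninfected; its definition also sets no minimum time after admission and differs from Section 1.2

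*SAP*

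**What the plan says.** **Definition.** Section 1.2 says that "any new sign of infection during hospital stay that was not present at admission will be considered as nosocomial infection", as a clinical diagnosis under the hospital's guidelines. It adds that after the interim analysis "the list of nosocomial infections was restricted to pneumonia, fever, UTI and sepsis". Section 9.3 words the rule differently: "Any new sign of infection during hospital stay that was not present at admission or not present for last 48 hours of hospital stay". A child is a case "if they have at least one of these four infections where symptoms started during the 10-day treatment period".

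**Analysis.** Section 9.3 states: "The proportion of subjects who have at least one suspected nosocomial infection in each treatment group will be compared using a logistic regression". Table 1 in Section 6.1 lists the model terms as treatment, sex, age and baseline weight-for-length Z score. There is no term for time observed or for infection at baseline. Section 9.3 allows the model to be omitted if infections are few.

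**Children who leave early.** Section 6.3 rules out imputation and says that data from children withdrawn for failure to respond, or "voluntary dropouts will be included in the analysis up to the time of withdrawal". An analysis without withdrawn children is mentioned there only as something that may be done. The ITT population in Section 4 needs just one post-baseline measure. Section 9.2 censors children who withdraw or die before they are ready for discharge. Section 9.3 has no such rule.

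**Admission illness.** Section 8.3 tabulates at Day 0 "type of diarrhoea and presence of pneumonia, sepsis/septicaemia, meningitis/encephalitis" and other diagnoses. Pneumonia and sepsis are also two of the four counted infections.

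**The concern.** There are two separate problems.

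**Time at risk.** The outcome is ever/never, so a child who leaves on Day 3 without infection enters the model as a full 10-day non-event. If one arm loses more children early, it has fewer days in which to record an infection and looks better for that reason alone. In an open-label study, unequal leaving is possible. The endpoint is called a rate, but nothing in the analysis uses time.

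**What counts.** Because the two conditions in Section 9.3 are joined by 'or', either is enough. A sign first seen hours after admission meets the first condition. The 48-hour condition does not delay the start of counting; it only adds signs that had been absent for 48 hours and returned. In acutely ill children some counted events may therefore belong to the illness that brought them in. Such events occur in both arms regardless of the oil and dilute any true effect. Section 1.2 has no 48-hour element, so the SAP gives two definitions of one endpoint.

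**Working it through.** The SAP gives no infection rate, withdrawal rate or power for this endpoint, so there is no figure of its own to reproduce. All rates below are assumptions chosen to show size.

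**1. How an event-free early leaver is scored.** The SAP never says it in words; it follows from three places. Section 4 admits the child to the ITT population. Section 6.3 keeps the child's data to withdrawal without imputation. Section 9.3 asks only whether an infection occurred. The answer is 'no', whatever the time observed.

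**2. Effect under a true null, everyone who leaves going at Day 4.** Assume a daily hazard of 2.5% in both arms.

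- Risk over 10 days: 1 − 0.975^10 = 0.2237. Risk over 4 days: 1 − 0.975^4 = 0.0963.
- Observed risk with fraction d leaving: (1 − d) × 0.2237 + d × 0.0963.
- d = 10%: 0.2109. d = 30%: 0.1855.
- Odds ratio, 30% arm against 10% arm: (0.1855/0.8145) ÷ (0.2109/0.7891) = **0.85**. For 20% against 10% it is 0.92.

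**3. The same with leaving spread evenly over Days 0 to 10.** Assume a 10-day risk R = 20%, so h = −ln(0.8)/10 = 0.0223.

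- Mean risk among leavers: 1 − (1 − e^(−10h))/(10h) = 1 − 0.2/0.2231 = 0.104.
- d = 10%: 0.9 × 0.20 + 0.1 × 0.104 = 0.190. d = 30%: 0.7 × 0.20 + 0.3 × 0.104 = 0.171.
- Odds ratio: **0.88**. For 20% against 10% it is 0.94.
- With R from 10% to 40%, 30% against 10% leaving gives 0.89 to 0.85.
- Equal leaving of 10% or 20% lowers the observed risk to 19.0% or 18.1%, and the odds ratio stays at 1.00.

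**4. Does using time at risk remove this?** In the model of step 2, expected days at risk are 0.2237/0.025 = 8.95 for a child who stays and 0.0963/0.025 = 3.85 for one who leaves.

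- d = 10%: 0.2109 events over 0.9 × 8.95 + 0.1 × 3.85 = 8.44 days, or 0.025 per day.
- d = 30%: 0.1855 events over 0.7 × 8.95 + 0.3 × 3.85 = 7.42 days, or 0.025 per day.

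The ratio is 1, provided that leaving is unrelated to infection risk.

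**5. Dilution by early signs of the admission illness.** Assume true risks of 20% and 12% (risk ratio 0.6), giving an odds ratio of (0.12/0.88)/(0.20/0.80) = 0.55.

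- If 20% of the control events are early and unaffected, the treated risk is 0.04 + 0.16 × 0.6 = 0.136 and the odds ratio is 0.63. At 10% and 30% it is 0.59 and 0.67.
- If instead a background of such signs with probability b is added to both arms, observed risk is 1 − (1 − p)(1 − b). At b = 10% this gives 28.0% and 20.8%, odds ratio 0.68. At b = 5% and 30% it is 0.62 and 0.79.

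Nothing in the SAP says which of these values, if any, is realistic.

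**The case against.** The case for leaving the plan alone has real force.

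- Only four infection types count, and the diagnosis is made clinically under hospital guidelines. A reader might infer that any sign counts and that the endpoint therefore fails to measure hospital-acquired infection. The SAP does not support that: clinical judgement may filter out signs of the admission illness, and even the early-event scenarios in step 5 leave 70% to 90% of control events open to a treatment effect. **This stands.**
- Early-leaver bias is hypothetical. It needs leaving that differs by arm or is related to infection, and no rates are given. **This stands**, and limits the point to a weakness in the plan, not a shown bias.
- Section 6.3 foresees an analysis without withdrawn children. In the simple models above that would also return a null result. But it is optional, and it discards infections recorded before withdrawal. **This stands in part.**
- A reader might want onset more than 48 hours after baseline to become the main definition. The 48 hours in Section 9.3 is a sign-free interval, not a delay, and the SAP does not state the gap between admission and baseline. If children had already spent time in hospital, such a rule could drop genuine hospital-acquired infections. **This stands**, so a 48-hour exclusion belongs in a sensitivity analysis.
- All analyses are labelled exploratory. That lowers the priority, but Section 6.2 advises caution about multiple p-values, which does not address unequal observation time.

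**Conclusion.** The point holds in a limited form. Section 9.3 ignores time at risk and has no rule for event-free early leavers, although Section 9.2 has one for discharge. With a 10-day risk of about 20% and 10% versus 30% leaving, a true null would appear as an odds ratio of about 0.85 to 0.88; with equal leaving unrelated to infection it would be 1. The arm with more leavers looks less infected, and the SAP gives no ground for saying which arm that would be.

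The missing minimum time after admission can dilute the odds ratio towards 1. Its size cannot be known from the SAP, and it should not be read as showing that the endpoint is invalid. Sections 1.2 and 9.3 do define the endpoint differently, and that needs no assumption.

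For an exploratory secondary endpoint this is a low-priority improvement.

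**What to change.** 1. In Section 9.3, analyse time to first suspected nosocomial infection, censored at leaving the study or at Day 10, with death treated as a competing event and the covariates already in Table 1. A count of infections with log days observed as offset is an alternative. Keep the logistic odds ratio as supportive, so the analysis now planned is still reported. Retain the provision for few events.
2. Reconcile the definitions in Sections 1.2 and 9.3, and say whether a sign that was present at admission, settled and returned is counted.
3. Add a sensitivity analysis that excludes onsets in the first 48 hours after admission, without replacing the main definition.
4. Tabulate early leaving by arm, day and reason next to this endpoint.

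**Cost.** Some added analysis work. Onset timing is already needed by "where symptoms started during the 10-day treatment period", and exit times are already needed for the censoring in Section 9.2. Item 3 also assumes that the time of admission is recorded, which the SAP does not state. Censoring assumes that leaving is unrelated to infection risk. That should be stated openly, because Section 6.3 includes withdrawal for failure to respond, where the assumption may fail. The change should be dated and recorded as made after the interim analysis.
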